#### B. Description of Population to be Enrolled:

##### Inclusion criteria:

- Age  $\geq 18$  to  $\leq 89$  years of age
- Actively receiving chronic peritoneal dialysis (receiving peritoneal dialysis treatments  $\geq 3$  times per week for  $\geq 3$  months)
- Ability and willingness to provide written informed consent before the first trial ready activity

##### Exclusion criteria:

- Patients currently receiving antimicrobial therapy or have received antibiotic therapy within 14 days prior to study
- Patients with known hypersensitivity reactions to dalbavancin or other glycopeptides
- Age <18 years old or >89 years old
- Prisoners
- Pregnant or breastfeeding women
- Decisionally challenged patients: Incompetent to consent, cognitively impaired (e.g. psychiatric disorder), altered decisional capacity due to the environment or situation (e.g. stress).
  - This will be evaluated based on previous medical history given from the patient and chart review
  - If altered decisional capacity is suspected due to environment or situation follow up questions will be asked by clinic personnel not involved with the study or direct care of the patient
- Patients with active peritonitis
- Temperature  $>38^{\circ}\text{C}$  or  $<36^{\circ}\text{C}$
- Significant abdominal tenderness
- Child-Pugh class B, or C

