### **II. Background and Significance:**

Every year in the United States approximately 110,000-115,000 patients are newly diagnosed with end-stage renal disease (ESRD) and begin treatment with renal replacement therapy. Nearly 10,000 of these patients are started on peritoneal dialysis (PD). The use of home dialysis has increased significantly (35% increase) in the last decade, with 95% of home dialysis patients undergoing PD. Infectious peritonitis is a leading major morbidity associated with PD, and it accounts for approximately 18% of infection-related mortality in PD patients. Severe or prolonged peritonitis can lead to peritoneal membrane failure, ultimately causing technical failure of PD and requiring transition to traditional hemodialysis methodologies. Rapid and effective treatment of peritonitis is required to reduce inflammation and preserve peritoneal membrane function. The current standard of care involves empiric antibiotics covering gram positive organisms as staphylococcus aureus, coagulase negative staphylococcus and enterococcus are common infecting pathogens. Vancomycin is commonly employed at most institutions as there is a risk of MRSA infections in this patient population. Addition of a second drug for gram negative bacteria coverage is recommended until culture and sensitivity results are available. Intravenous or intraperitoneal administration of antibiotics can be utilized; however, guidelines recommend the intraperitoneal administration of antibiotics with a dwell time of at least 6 hours because it provides instant, high, and sustained concentrations of the antibiotic in the peritoneal fluid. Although vancomycin covers the majority of gram positive organisms that cause peritonitis, its use can be cumbersome in PD patients. Plasma vancomycin drug concentration monitoring must occur to evaluate for vancomycin accumulation. Additionally, vancomycin must be re-administered every 3-5 days in order to maintain steady-state trough concentrations around 15 mcg/ml. Similarly to vancomycin, dalbavancin interferes with cell wall synthesis. This is done through binding of the D-alanyl-D-alanine terminus of the cell wall peptidoglycan. Dalbavancin has been shown to rapidly reach therapeutic systemic concentrations and to have an extended half-life of ~8.5 days. Dalbavancin has been shown safe and effective with a treatment doses of 1500 mg once or 1000 mg followed by a 500 mg dose on day 7. Dalbavancin pharmacokinetics were evaluated in patients who had hepatic or renal impairment. This study showed compared to healthy subjects dalbavancin exposure was not increased in mild renal impairment, exposure was ~50% higher in moderate renal impairment, 100% higher in severe renal impairment, and not significantly different in end stage renal disease

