**D. Description, Risks and Justification of Procedures and Data Collection Tools:**

**Enrollment and Screening:** Study subjects will be contacted an enrolled through [name] clinic. Initial contact will be made by phone prior to a clinic appointment to discuss initial interest of the patient. Further information and enrollment will take place at a clinic visit or time of the patients choosing. Enrollment will take place in a private room at [name] clinic. Initial baseline and demographic information will be gathered for enrolled patients at the time of enrollment. Safety labs (comprehensive metabolic panel and urine pregnancy test for women of childbearing potential) will be drawn or performed at [name] clinic and will coincide with a scheduled clinic visit closest to study protocol initiation. The comprehensive metabolic panel will be drawn to evaluate Child-Pugh score if there is no comprehensive metabolic panel within the medical record within 30 days of protocol initiation.

**Visit 1 and 4:** (~8 hours): On visits 1 and 4 the patients will undergo intensive PK sampling. Inclusion and exclusion criteria will be reviewed with the patient at each visit prior to initiation of the protocol. Subjects will be admitted to the CTRC in the morning and a "saline-lock" will be placed. The dalbavancin preparations will be prepared and managed by [name] or [name] who are both clinical pharmacists with training in sterile drug preparation. The dalbavancin 1500 mg will either be administered, by CTRC nursing staff, intravenously (as randomly assigned) or into the intraperitoneal space (as randomly assigned) using the patient's existing peritoneal dialysis catheter with the patients currently prescribed dialysate. Following the blood and peritoneal fluid collection at the second dialysis volume exchange, the subjects will be discharged and asked to return at a scheduled time on day 7. Patients will also be given a specimen collection up with instructions to collect approximately 30 ml of peritoneal dialysate following their evening nocturnal dwell. The collected dialysate will be returned to the investigators.

**Visit 2, 3, 5, and 6:** (~60 minutes): A "saline-lock" will be placed and a single blood and peritoneal fluid sample will be collected at each of these visits. All blood and peritoneal fluid draws will be

completed at the outpatient CTTC. The patient will be discharged and follow up visits will be scheduled for day 14 or next intensive PK sampling visit.

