**Washout:** During the 45 day or greater washout portion of this study the patients will not be asked to come in for any visits. This timeframe, which is greater than 5 half-lives of dalbavancin, is to ensure that all of the medication (dalbavancin) has left the patients' system before administering another dose of the medication.

**Laboratory tests:** The laboratory tests to be performed as part of this study include pregnancy testing to confirm eligibility and comprehensive metabolic panels if one is not documented within 30 days prior to the initiation of protocol to determine Child-Pugh score. These will be done at an initial screening visit if required to coincide with clinic appointment before visit 1.

**Pharmacokinetic Assessments:** 4 mL of blood will be collected in a purple top (EDTA) tube and 4 mL of peritoneal fluid in a urine collection cup at pre-dose, and 1, 2, 3, 4, 6, dialysis volume exchange. Blood and peritoneal fluid will be placed in an ice bath to chill until centrifuged. Plasma will be harvested within 30 minutes of each blood sample and will be stored at -80°C until assaying.

**Sample Coding and Storage:** Study samples will be coded with an indirect identifier and stored in [name] access-controlled laboratory.

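### The 14-day antibiotic look-back can admit a patient with residual dalbavancin at the first study dose, and the analysis plan has no rule for a non-zero pre-dose concentration

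*Combined protocol and SAP*

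**What the plan says.** Section IV.B (Exclusion criteria) has one bullet on earlier drug exposure: "Patients currently receiving antimicrobial therapy or have received antibiotic therapy within 14 days prior to study". The only criterion that names dalbavancin concerns allergy: "Patients with known hypersensitivity reactions to dalbavancin or other glycopeptides". No bullet asks when a patient last received dalbavancin.

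Section IV.D (Washout) sets at least 45 days between the two study periods and gives the reason: "This timeframe, which is greater than 5 half-lives of dalbavancin, is to ensure that all of the medication" is gone before the next dose. Section II gives the half-life used here: "extended half-life of ~8.5 days".

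Sections IV.C and IV.D both call for a plasma and a peritoneal fluid sample before dosing on day 0, to be assayed for dalbavancin. Both say that samples are kept at -80°C until assay. Under Visit 1 and 4, Section IV.D adds: "Inclusion and exclusion criteria will be reviewed with the patient at each visit prior to initiation of the protocol".

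Section IV.F (Pharmacokinetic analysis) computes AUC by the linear trapezoidal method and systemic clearance as F × Dose / AUC. It mentions no baseline subtraction, no exclusion threshold and no carryover term. The two routes are then compared within patients by a paired t-test with n = 10.

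**The concern.** The study drug is also the analyte, so any dalbavancin already in the body is counted as if it came from the study dose. The protocol guards against this between periods but not before the first. Its own hypothesis in Section I is that one 1500 mg dose keeps plasma and peritoneal concentrations adequate for two weeks. If that is right, a 14-day look-back can admit someone whose concentrations were still adequate the day before they became eligible.

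Residual drug would raise that patient's period-1 concentrations, Cmin and AUC, and lower the calculated clearance. Little of it would be left by period 2, so the patient's IV/IP difference would be distorted. The two-week concentrations, which bear most directly on the hypothesis, would also be too high.

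**Working it through.** **Inputs.** Half-life h = 8.5 days (Section II); look-back 14 days, so day 15 is the first day clearly admitted (Section IV.B); washout at least 45 days (Section IV.D); n = 10 (Section IV.C). Assumptions that the documents do not supply: mono-exponential decay, and an earlier dose giving the same exposure as the study dose.

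**The plan's own figure.** 5 × 8.5 = 42.5 days, and 45 / 8.5 = 5.29 half-lives. The statement that 45 days exceeds five half-lives is correct.

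**Fraction remaining** = 2^(−t/h):

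| Days since earlier dose | Half-lives | Remaining |
|---|---|---|
| 14 | 1.65 | 31.9% |
| 15 | 1.76 | 29.4% |
| 30 | 3.53 | 8.7% |
| 45 | 5.29 | 2.5% |

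Moving from day 15 to day 45 cuts the residual by 0.294 / 0.0255 ≈ 11.5-fold.

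**Sensitivity to the half-life.** For an assumed 7 to 12 days, the residual is 22.6% to 42.0% at day 15 and 1.2% to 7.4% at day 45.

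**Effect on one patient.** With residual fraction r and elimination rate k, the leftover drug adds r × C0 / k to an AUC0-∞ of C0 / k. The relative inflation is therefore r, or 29.4% at day 15. If period 1 is IV, clearance is understated by 1 − 1/1.294 = 22.7%. If period 1 is IP with absorbed fraction F below 1 and the earlier dose was IV, the relative inflation is 29.4% / F. The documents give no value for F.

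**Effect by period 2.** Taking the shortest reading, 45 days from dose to dose, the outside dose is 15 + 45 = 60 days old, and 2^(−60/8.5) ≈ 0.75%. The contamination therefore falls almost wholly in period 1.

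**Effect on the mean.** One affected patient among 10 with similar AUCs gives 29.4% / 10 ≈ 2.9%. No expected AUC is given, so this cannot be put in mg·hr/L or set against the stated detectable difference.

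**The case against.** The strongest reply is that the event is hypothetical. Nothing shows that any of the 35–40 clinic patients has received dalbavancin. Section II describes vancomycin as the usual agent for peritonitis, and Section IV.E says dalbavancin is not established for that use. The 29% is also a worst case: at day 30 the same formula gives 8.7%, and the plan will explore models with more than one compartment. This stands, and it limits the weight of the point.

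A reader might infer several stronger things that the documents do not support:

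- **That the carryover would go unmeasured.** It would not, because a pre-dose sample is assayed in both fluids. What is missing is a rule for using the result, and a result before dosing: nothing requires the assay to be read first.
- **That the two intervals contradict each other for the same purpose.** The 14-day bullet has no stated purpose and may be an infection screen. The inconsistency is one of effect: no rule secures a drug-free baseline in period 1.
- **That the terminal half-life would be biased.** Under mono-exponential decay the residual falls at the same rate as the new dose, so the slope is unchanged.
- **That one route is systematically favoured.** Order is randomised, so one affected patient could shift the comparison either way.
- **That antibiotics taken during the washout escape the criteria.** The repeated eligibility review at visit 4 largely answers this. The wording is only unclear about which date the window counts back from.
- **That study doses are at least 59 days apart.** That holds only if the 45 days start after visit 3 (14 + 45 = 59). The documents do not settle when the washout starts, and the point does not need the figure.

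**Conclusion.** The point holds in a limited form. As written, the criteria can admit a patient with about 29% of an earlier equal dose still present (about 23% to 42% for half-lives of 7 to 12 days). The protocol's own standard before another dose leaves about 2.5%. The pre-dose sample would reveal the residual but would not prevent dosing, and Section IV.F gives no correction or exclusion.

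The consequence is a period-1 AUC up to about 29% too high in that patient and a 10-patient mean about 3% too high. These figures assume mono-exponential decay, equal exposure from the earlier dose, a gap of 15 days, one affected patient and similar AUCs across patients. Because the trigger is probably rare, this is a cheap improvement and not a threat to the study as a whole.

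**What to change.** 1. **Section IV.B.** Keep the antimicrobial bullet, but make clear that its 14 days count back from each study dose (visits 1 and 4). Add a bullet, for example: *Receipt of dalbavancin outside the study within 45 days before visit 1, or at any time between visit 1 and visit 4.* This applies the protocol's own minimum washout interval to the same drug.
2. **Section IV.F.** State that, for any patient with a quantifiable pre-dose concentration, AUC and the paired IV/IP comparison will be corrected for the residual. This means subtracting C_pre × e^(−Kel·t) from each later concentration, using that patient's Kel. For AUC0-∞ it removes C_pre / Kel. Add a sensitivity analysis that leaves the patient out. The rule also covers any residue from the first study dose seen before the second.

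**Cost.** One eligibility sentence and one analysis sentence, with no extra samples because the pre-dose sample is already planned. A rare affected patient waits (from day 15 to day 45, 30 further days at most) or is not enrolled. A patient given dalbavancin outside the study between visits 1 and 4 would no longer qualify at visit 4, and that pair would be lost.

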#### C. Study Design and Research Methods

This study is an open label, cross-over study, evaluating the plasma and peritoneal fluid pharmacokinetics of dalbavancin after either intravenous or intraperitoneal administration. The

patients will be randomly assigned to receive dalbavancin either intravenously or intraperitoneally on study visit 1. The patients will receive the alternate administration technique following the washout period at visit 4. Patients will be administered dalbavancin either intravenously or intraperitoneally on study day 0. Pharmacokinetic analysis will be conducted on days 0, 7, and 14. Following the wash out period of 45 days or greater, the same 10 patients will cross-over and then be administered dalbavancin via the alternate administration technique received in visit 1 on study day 0. Pharmacokinetic analysis will be conducted again on days 0, 7, and 14. (see Appendix 1)

*Sample Size:*

Ten (n=10) patients will be evaluated in this pharmacokinetic evaluation. Since this is a descriptive pharmacokinetic study a sample size calculation was not performed

*Plasma and peritoneal fluid sampling:*

Dalbavancin will be administered on study day 0. On the intravenous administration day dalbavancin will be administered as a 30-minute IV infusion. On the intraperitoneal administration day, dalbavancin will be administered in the peritoneal dialysis fluid with a 6 hour dwell time. On day 0, patients will undergo plasma and peritoneal fluid pharmacokinetic sampling for determination of dalbavancin concentrations at time zero, 1 hour, 2 hours, 3 hours, 4 hours, 6 hours, at time of volume exchange. Patients will be given a specimen collection cup and asked to collect ~30 ml of peritoneal dialysate following scheduled nocturnal dwell approximately 24 hours following the administration of dalbavancin administration. Patients will report for a single PK measurement on study days 7 and 14. (18 total plasma and 18 total peritoneal fluid samples per patient). Blood samples will be drawn from a peripherally inserted intravenous catheter. Peritoneal fluid samples will be drawn from the already placed peritoneal dialysis catheter. Blood samples will be immediately centrifuged at 3000g and plasma and peritoneal fluid samples will be stored at -80°C until analysis.

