##### *Pharmacokinetic analysis:*

Plasma and peritoneal fluid concentration-time data for dalbavancin will be evaluated using a multi-compartment model in Phoenix WinNonlin (Pharsight corporation). One, two, and three compartment models will be explored. The following PK parameters will be calculated for plasma and dialysate samples: Cmax – measured, Tmax – measured, Cmin – measured. Fraction of intraperitoneal (IP) dose absorbed [(Dose – drug concentration remaining in dialysate at end of

antibiotic dwell)/Dose].  $K_{el}$  – elimination rate constant.  $T_{1/2} = 0.693/K_{el}$ .  $K_{pc0-6}$  – rate constant for distribution of dalbavancin from peritoneal cavity between 0-6 hours. Distribution half-life in the peritoneal cavity between 0-6 hours ( $t_{1/2} = \ln 2/k_{pc0-6}$ ). Clearance systemic =  $(F \times \text{Dose})/AUC_{0-\infty}$ . Clearance peritoneal – dalbavancin concentration in spent dialysate/AUC of peritoneal fluid. Non-dialysis clearance –  $Cl = Cl_{plasma} - Cl_{peritoneal}$ .  $AUC_{0-\infty}$  – linear trapezoidal method.  $AUC_{0-12}$  hours – linear trapezoidal method. Volume of distribution for each compartment –  $Cl/k_{el}$ ; nonsteady state equations will be utilized. The ratio of plasma dalbavancin to dialysate plasma concentration at each time point –  $C_{plasma}/C_{dialysate}$  and via  $AUC_{plasma}/AUC_{dialysate}$ . Given the sample size of 10 patients completing each treatment modality we will be able to calculate means and standard deviations for all included pharmacokinetic parameters. We will incorporate the dalbavancin PK parameters into a nonlinear mixed effects model (NONMEM) or ADAPT II to determine the pharmacokinetics and examine the effects of varying dosing strategies on plasma and peritoneal fluid concentrations.

*Analysis of pharmacodynamic targets:*

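### Plasma elimination rate rests on two late samples per period, and the visit 4 pre-dose sample, already collected, has no stated role in estimating it

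*Combined protocol and SAP*

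**What the plan says.** On each dosing day, section C asks for "concentrations at time zero, 1 hour, 2 hours, 3 hours, 4 hours, 6 hours, at time of volume exchange". After that, "Patients will report for a single PK measurement on study days 7 and 14". Patients also "collect ~30 ml of peritoneal dialysate following scheduled nocturnal dwell approximately 24 hours following the administration", but this sample is dialysate only, so no plasma is taken between the dosing visit and day 7.

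Section D repeats the dense sampling in both periods: "On visits 1 and 4 the patients will undergo intensive PK sampling". Its Pharmacokinetic Assessments paragraph says "4 mL of blood will be collected in a purple top (EDTA) tube", with peritoneal fluid, "at pre-dose, and 1, 2, 3, 4, 6, dialysis volume exchange". Visit 4 therefore includes a blood and a peritoneal fluid sample taken before the second dose. The washout lasts at least 45 days with no stated maximum, and no visits take place during it.

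Under Pharmacokinetic analysis in section F, K_el is listed only as "elimination rate constant". Half-life is 0.693/K_el, volume is clearance divided by K_el, and systemic clearance uses AUC0-∞. One-, two- and three-compartment models are to be explored, followed by a population model. The plan does not say which points determine K_el or how a model is chosen. Section C places the pharmacokinetic analysis on days 0, 7 and 14 of each period. No text gives the visit 4 pre-dose value a role in the period 1 decline, and none excludes it.

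**The concern.** Two samples less than one half-life apart give a weak estimate of a slow elimination rate, and with two points the fit cannot be checked. The uncertainty passes into half-life and volume, and into the part of AUC0-∞ that lies beyond day 14. It reaches clearance through AUC0-∞. These are listed outputs of the study's primary pharmacokinetic endpoints.

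The design already collects a plasma sample far out on the decline from dose 1. If the analysis stays within days 0, 7 and 14, it gives up most of the information that the study will hold on the period 1 elimination rate. It also leaves unused a direct measurement of how much drug remains when period 2 starts.

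**Working it through.** **Inputs from the documents.** Half-life about 8.5 days (Background and Significance); late plasma samples on days 7 and 14; washout of at least 45 days. **Assumed.** CV per concentration of 5–20%, taken as the SD on the log scale, because the documents give neither assay error nor a quantification limit.

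**1. The plan's own figures.**
- Plasma count: (7 day-0 times + day 7 + day 14) × 2 periods = 18. This reproduces the plasma part of "18 total plasma and 18 total peritoneal fluid samples per patient" and confirms two plasma samples per period after day 0.
- Peritoneal count: with the 24-hour sample, (7 + 1 + 2) × 2 = 20, not 18. The two-sample count therefore applies strictly to plasma.
- Washout: 45/8.5 = 5.29 half-lives, which agrees with the plan's statement that it exceeds five.

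**2. When the visit 4 pre-dose sample falls.** Washout contains no visits, and Appendix 2 places it after visit 3 (day 14). Visit 4 is then at day 14 + 45 = 59 or later after dose 1. Day 45 would apply only if washout were counted from dose 1. Expected residual is 2^(−59/8.5) = 0.8% of the back-extrapolated starting level, or 2^(−45/8.5) = 2.5%.

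**3. Two-point slope.** K = ln 2/8.5 = 0.0815 per day, and SE(K) = CV/√Sxx. For days 7 and 14, Sxx = 3.5² + 3.5² = 24.5. At 10% CV, SE(K)/K = 0.10/√24.5/0.0815 = 24.8%, with 2 − 2 = 0 residual df. The interval is 7/8.5 = 0.82 half-life.

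**4. Adding the visit 4 pre-dose value** (residual df 3 − 2 = 1).
- Days 7, 14, 59: Sxx = 1592.7, so 0.10/√1592.7/0.0815 = 3.1%.
- Days 7, 14, 45: Sxx = 818, so 0.10/√818/0.0815 = 4.3%.

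| Points | CV 5% | CV 10% | CV 15% | CV 20% | 95% range of estimated half-life, true value 8.5 days, CV 10% |
|---|---|---|---|---|---|
| 7, 14 | 12.4% | 24.8% | 37.2% | 49.5% | 5.7–16.5 days |
| 7, 14, 45 | 2.1% | 4.3% | 6.4% | 8.6% | 7.8–9.3 days |
| 7, 14, 59 | 1.5% | 3.1% | 4.6% | 6.1% | 8.0–9.0 days |

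**5. Share of AUC0-∞ beyond day 14.** For a mono-exponential decline, 2^(−14/8.5) = 32%.

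**6. Does a compartment fit help?** I took eight post-dose plasma times (1, 2, 3, 4, 6 h, the exchange assumed at 8 h, days 7 and 14), sums of exponentials and 10% CV. Residual df are 8 − 2 = 6, 8 − 4 = 4 and 8 − 6 = 2 for one, two and three compartments. Relative SE of the terminal rate:
- One compartment: 9.0%, falling to 2.2% with day 59 added.
- Two compartments, distribution half-life 0.25 or 0.5 day (assumed): 24.7–24.8%, falling to 3.1%.
- Two compartments, distribution half-life 1 day (assumed): 39.8%, falling to 3.5%.

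With two compartments, the day 0 samples add almost nothing to the terminal rate.

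**7. Leverage of the added point.** 1/3 + (59 − 26.67)²/1592.7 = 0.99; for day 45 it is 1/3 + (45 − 22)²/818 = 0.98.

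**The case against.** The plan does not commit to a two-point regression. It names compartment models, which have residual df overall, and a population model that borrows across patients and could take in the visit 4 sample. Results are to be summarised as means over 10 patients, so at 10% CV the measurement contribution to a mean K_el is about 24.8%/√10 = 7.8%. Even without the extra sample, a slope shared across a patient's two periods would have a relative SE of 24.8%/√2 = 17.5%. The added point is the lowest concentration, nearest an unstated assay limit, and with leverage near 1 its single df hardly tests log-linearity.

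Much of this stands. The fault is an unstated use, and a reader who infers that the plan has decided to discard the sample, or to keep it only as the period 2 baseline, goes further than the text. The model argument is weaker: a two-compartment fit leaves the terminal rate as imprecise as the two-point line, there is no model-selection rule, and the population model is not said to use the value.

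Three further inferences are tempting and not supported:
- **That the two-week hypothesis depends on half-life.** Day 14 concentrations are measured directly in both fluids, and target attainment is built from Cmax and AUC0-12. None of these needs K_el.
- **That individual half-lives would be mostly measurement error.** This needs the between-patient variability of half-life, which the documents do not give.
- **That the better period 1 slope can simply be carried into period 2.** This would make the route difference in K_el zero by construction, although the plan compares routes within patients, and would impose one route's slope on the other's AUC tail.

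**Conclusion.** The point holds in a limited form. With the planned plasma samples, a patient's K_el in one period has a relative SE of about 25% at 10% CV (12–50% for 5–20%), under a log-linear terminal fit or a two-compartment fit with a distribution half-life of 0.5 day or less. It affects K_el, half-life, volume and the extrapolated share of AUC0-∞, about 32% if decline is mono-exponential. Entering the visit 4 pre-dose value would bring the period 1 figure to about 3% (day 59) or 4% (day 45).

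This rests on the protocol's 8.5-day half-life, an assumed constant CV, log-linear decline from day 7 to visit 4, and a quantifiable value. The last cannot be settled from the documents. At day 59 the expected level is about 1.2 mg/L for 1500 mg in an assumed 10 L (150 × 0.0081), or 0.4 mg/L with 50% absorbed and 15 L (50 × 0.0081). A slower late phase would bias the slope. Period 2 gains no late point of its own. The residual carried into period 2 is also small, about 0.8% at day 59, so the main gain is precision in period 1. The change is worth making, but the study's central question does not turn on it.

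**What to change.** In the Pharmacokinetic analysis text of section F, state that:
- the visit 4 pre-dose concentration enters the analysis at its actual time since dose 1, as a period 1 terminal point;
- both periods are fitted jointly with the full dosing history, so that residual drug from dose 1 is carried into period 2;
- K_el may differ by route, and the period 1 value is not imposed on period 2;
- a pre-dose value below the assay limit is treated as censored, and the limit is reported;
- the fit is checked for a slower late phase, with K_el also shown without the added point because of its leverage.

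The cost is a few sentences of analysis text and a joint model in software of the kind already named. No sample or visit is added. Precision will differ between a patient's two periods, and this should be stated when routes are compared.
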